15.0 Recruitment Methods

15.1 Subjects will be recruited from the pain clinic at RIC. Furthermore, flyers, or the RIC. Interested participants will be directed to research staff who will inform them of the time commitment required and questioned regarding the inclusion/exclusion criteria. Once subjects have agreed to participate in the study, they will come to RIC for further participation instructions.

15.2 Subjects will be paid through the Clincard system if enrolled past the consenting and screening phase of the study. If subjects only come in for one visit they will be paid through petty cash. . Subjects will be compensated up to \$100 for completing the study. Subjects will be compensated \$50 for the first session and \$50 for the second session. However, in the event that protocol needs to be spread across three sessions, subjects will be paid \$50 for the first session and \$25 for the second and third session.

16.0 Local Number of Subjects

The total number of subjects to be enrolled will be 30. We will enroll 30 participants who use a walker due to back pain and 30 older adults who use a walker.

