3.0 Inclusion and Exclusion Criteria

3.1 We will recruit 30 subjects. Most subjects will be recruited through RIC recruitment flyers and from the RIC pain clinic.

Inclusion:

- Individuals using a walker with or without back pain for ambulation.
- Ages from 18 to 89 years old
- Medically stable for therapy

Exclusion

- Patient weight exceeds 300 lbs
- Patient height is below 5'0" or exceeds 6'3"
- Inactive, physically unfit to fit into the device.
- Cognitive deficits or visual impairment that would impair their ability to give informed consent or to follow simple instructions during the experiments.
- MMSE score below 17
- Pregnant women
- Co-morbidity that interferes with the study (e.g. stroke, pace maker placement, severe ischemia cardiac disease, etc.)

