4.0 Study-Wide Number of Subjects

This study will enroll up to 30 older adults who use walkers as a primary mode of transportation, and 30 individuals who use a walker due to low back pain.

[figure not shown]

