5.0 Study-Wide Recruitment Methods

This study will enroll up to 30 eligible subjects. RIC approved flyers will be posted at RIC in-patient, out-patient, day rehabilitation and fitness facilities, as well as pain clinic offices, providing contact information of study recruiters. Authorized research personnel will identify potential subjects from RIC's Cerner Information Systems. Patients will be

PROTOCOL TITLE: Life Walker vs. Conventional Rollator and Predicate Mobility Device

considered enrolled into the study after they have signed the Consent Form and HIPAA Authorization for Research.

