6.0 Study Timelines: 1-2 days of training

PROTOCOL TITLE: Life Walker vs. Conventional Rollator and Predicate Mobility Device

Achievable benchmarks include: (1) recruitment of 30 subjects who use a walker and 30 subjects older adults who use a walker; (2) appropriate functional training of the LifeWalker Upright for all of the enrolled participants ; (3) completed clinical, performance outcome and self report measures for all of the of subjects.

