13.0 Setting

- 13.1** Procedures will be performed in the clinical laboratory housed in a Rehabilitation inpatient and outpatient hospital.

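### Section 16.0 sets total enrolment at 30 and then enrols 30 + 30 = 60, and the other sections of the protocol split between the two figures

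*Protocol*

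**What the plan says.** The protocol gives the number of subjects in five places.

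- **Section 16.0, across its two sentences:** "subjects to be enrolled will be 30. We will enroll 30 participants who use a walker due to back pain and 30 older adults". The first sentence, "The total number of subjects to be enrolled will be 30", gives the total; the second, "We will enroll 30 participants who use a walker due to back pain and 30 older adults who use a walker", gives the groups.
- **Section 3.1:** "We will recruit 30 subjects".
- **Section 5.0:** "This study will enroll up to 30 eligible subjects".
- **Section 4.0:** "This study will enroll up to 30 older adults who use walkers as a primary mode of transportation, and 30 individuals who use a walker", the second group being those whose reason is low back pain.
- **Benchmarks under Section 6.0:** "recruitment of 30 subjects who use a walker and 30 subjects older adults who use a walker".

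On the setting, Section 13.1 states: "Procedures will be performed in the clinical laboratory housed in a Rehabilitation inpatient and outpatient hospital". Eligibility in Section 3.1 covers ages 18 to 89 and walker users whether or not they have back pain.

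**The concern.** A total of 30 cannot be made up of 30 people in one group and 30 in another unless the groups are the same people. The visible protocol contains no other sample-size figure, so nothing else in it shows which number was meant.

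The practical problem is when to stop enrolling. A team that stops at 30 falls short of the second sentence of Section 16.0 and of the benchmark under Section 6.0. A team that enrols an eligible 31st subject exceeds Section 5.0 and the first sentence of Section 16.0. The statistical problem is that the number of subjects contributing to the within-subject comparison of devices could be 30 or 60, and the precision of the primary comparison depends on which it is.

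**Working it through.** **Step 1. The stated total against the sum of its parts (Section 16.0).**

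Stated total: 30. Groups: 30 with back pain and 30 older adults.

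30 + 30 = 60, and 60 / 30 = 2.

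The stated total is not reproduced. The gap is 30 subjects, too large for rounding.

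**Step 2. The sections side by side.**

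| Place | Figure | Implied total |
|---|---|---|
| 3.1 | 30 | 30 |
| 5.0 | up to 30 | ceiling of 30 |
| 16.0, first sentence | 30 | 30 |
| 4.0 | up to 30, and 30 | ceiling of 60 |
| 6.0, benchmark | 30 and 30 | 60 |
| 16.0, second sentence | 30 and 30 | 60 |

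Three statements support 30 and three are written as two groups of 30. Section 4.0 is the weakest of the second set. Its wording sets a ceiling, so it conflicts with the ceiling in Section 5.0 but does not by itself require 60.

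**Step 3. Readings that might reconcile the figures.**

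- *Study-wide versus local.* This fails. The two study-wide sections disagree with each other (4.0 allows 60, 5.0 allows 30), the local section holds both figures, and Section 13.1 describes a single laboratory in one hospital.
- *30 means 30 per group.* This fails. Section 16.0 calls 30 the total, and Sections 3.1 and 5.0 mention no groups.
- *The groups overlap completely.* Arithmetically this works: 30 people counted in both groups make 30. It requires every subject to be an older adult who also uses a walker because of back pain. No visible passage says so. Sections 4.0 and 16.0 list the groups as separate counts, and the eligibility criteria admit younger adults and people without back pain.

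**Step 4. What the factor of two means for precision (scale only).**

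The protocol states no alpha, power, effect size, standard deviation or test, so neither 30 nor 60 can be derived from it. The following are assumptions: a paired t test on two devices, two-sided, no loss, 80% power, all subjects analysed together.

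Power is approximately P(T > t_crit), where T has a noncentral t distribution with n − 1 degrees of freedom and noncentrality d√n. Here d is the mean paired difference divided by the standard deviation of the differences, and t_crit is the 1 − alpha/2 quantile of the central t. Solving for 80% power gives:

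| Alpha | Detectable d, n = 30 | Detectable d, n = 60 | Power of n = 30 at the n = 60 value of d |
|---|---|---|---|
| 0.05 | 0.529 | 0.368 | 0.495 |
| 0.05/2 = 0.025 | 0.589 | 0.407 | 0.456 |

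The second row assumes alpha is split over two comparisons, Life Walker against each of the other two devices.

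**Step 5. Payments (Section 15.2, up to 100 dollars per subject).**

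30 × 100 = 3,000 dollars; 60 × 100 = 6,000 dollars.

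**The case against.** Nothing visible removes the contradiction inside Section 16.0. The best case on the other side concerns how far its consequences reach.

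- *Full overlap would let 30 comply.* This is correct as logic, so the statement that no total complies holds only if complete overlap is excluded. The reading is unstated and fits poorly with the eligibility criteria.
- *A missed benchmark is not a protocol breach.* This is fair. The benchmark under Section 6.0 is described as achievable, not mandatory. It may also belong to a different section, since the visible numbering passes from 6.0 to 8.0. The second sentence of Section 16.0 is enough without it.
- *Section 5.0 caps eligible subjects but counts people as enrolled at consent, before eligibility is checked (Section 8.0).* A 31st person who consents and then fails screening would therefore not exceed that cap. This is true, but screen failures do not explain 30 against 60.
- *The protocol does not say that the two groups are pooled.* This is also true. If they were analysed separately, 30 + 30 would mean 30 per analysis and the n = 60 column would not apply. Pooling is a reasonable reading, because the primary objective in Section 1.0 names one population with or without back pain, but it remains an assumption.
- *The power figures rest wholly on assumptions.* They do, and they serve only to show scale. The contradiction does not depend on them.
- *A figure after Section 4.0 is not shown.* Its content is unknown, and it could not undo the conflict between two printed sentences in Section 16.0.

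**Conclusion.** The concern holds and must be fixed. Total enrolment is 30 or 60, and the protocol does not settle which. That rests on the printed text and one addition, with a single qualification: complete overlap of the two groups, which no visible passage states, would make 30 consistent.

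Under the assumptions listed in the working, the choice moves the detectable standardised difference from 0.53 (30 subjects) to 0.37 (60 subjects) at alpha 0.05, or from 0.59 to 0.41 at alpha 0.025. A difference that 60 subjects would detect with 80% power would be detected by 30 with about 49% or 46% power respectively.

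**What to change.** The sponsor chooses one total and states it identically in Sections 3.1, 4.0, 5.0, 6.0 and 16.0. There are two ways to do this:

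- **60:** written as 30 per group. The totals in Sections 3.1, 5.0 and the first sentence of 16.0 are corrected. Maximum subject payments are 6,000 rather than 3,000 dollars, and the number of subjects to be tested in the laboratory is twice that under a total of 30.
- **30:** the two-group statements in Sections 4.0, 6.0 and the second sentence of 16.0 are replaced by the intended split. Only text changes.

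A minor point for the same edit: use the same group labels in Sections 4.0, 6.0 and 16.0. Section 6.0 leaves out back pain, and none of the three says which group an older adult with back pain counts toward.

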17.0 Confidentiality

All personal information (names, addresses, email or phone numbers, etc.) gathered for this study that can identify participants will be kept secure to protect their privacy and will never be shared at any time with any person or entity. Data collected during the study and shared with others will reference participants only by an alphanumeric code. The “master list” linking personal information to the alphanumeric code will not be shared, and will be kept by the study PI in a secure location. All personal information linking participants to their data will be destroyed after three years (or according to RIC compliance procedures) following the completion of the study. De-identified information gathered from participants will be used by RIC.

18.0 Provisions to Protect the Privacy Interests of Subjects

Every possible precaution will be taken to protect the privacy interests of subjects. Participation in this study is completely voluntary. Trained research personnel will explain the purpose of the study and intended use of subject’s personal health information and precautions taken to keep the study information and data confidential.

PROTOCOL TITLE: Life Walker vs. Conventional Rollator and Predicate Mobility Device

19.0 Compensation for Research-Related Injury

If the research involves more than Minimal Risk to subjects, describe If the subject gets an injury or illness as a result of study, subject is required to promptly notify the PI of the study about the illness or injury. The hospital [Researchers, RIC, Northwestern University and all affiliated clinical sites] will provide the basic immediate clinical care needed, however, any advanced or long-term clinical care will not be provided. Furthermore, any costs related to medical care required because of a bad outcome resulting from participation in this research study will not be compensated by the study PI or associated organization. However, this does not keep subject from seeking to be paid back for care required because of a bad outcome.

20.0 Process to Document Consent in Writing

20.1 Informed consent will take place at RIC's Rehabilitation Technologies and Outcomes Lab in room 1771.

20.2 Trained research personnel will guide the subject through consenting process. Subject will be given detailed explanation of the purpose, time line, commitment, procedures, data handling and privacy and confidentiality of information pertaining to the study.

21.0 Drugs or Devices

21.1 Classification - type of device: Rolling Walker

21.2 Storage and stability: Device is stored at RIC Flagship hospital-Room #1771. The device is accessible only to research staff.

21.3 Availability: Property of the Rehabilitation Technologies and Outcomes Research Lab at RIC.

PROTOCOL TITLE: Life Walker vs. Conventional Rollator and Predicate Mobility Device
